## 6.8. Patient Characteristics

Baseline characteristics will be summarized for the randomized population by treatment group and overall. Summaries will include descriptive statistics for continuous and categorical measures. Fisher's exact test or Pearson's chi-square test will be used for treatment-group comparisons of categorical data. For continuous data, analysis of variance (ANOVA), with independent factors for treatment, will be used. Patient characteristics to be presented include:

- age
- gender

- race
- ethnicity
- height
- body weight
- body mass index (weight (kg) / [height (m)])
- tobacco use
- alcohol use
- years of education
- work status
- time since onset of first AD symptoms
- tau PET burden (various measures)
- time since diagnosis
- APOE4 carrier status (carrier [ $\epsilon 2/\epsilon 4$ ,  $\epsilon 3/\epsilon 4$ ,  $\epsilon 4/\epsilon 4$ ], noncarrier [ $\epsilon 3/\epsilon 3$ ,  $\epsilon 2/\epsilon 2$ ,  $\epsilon 3/\epsilon 2$ ])
- APOE4 genotype ( $\epsilon 2/\epsilon 4$ ,  $\epsilon 3/\epsilon 4$ ,  $\epsilon 4/\epsilon 4$ , no  $\epsilon 4$ )
- having 1 or more first degree relatives with AD
- AChEI and/or memantine use at baseline

Baseline severity of impairment as measured by ADAS-Cog13, ADCS-ADL total score and instrumental (ADCS-iADL) and basic subscores (ADCS-bADL), CDR Sum of Boxes, MMSE, Cogstate Brief Battery (CBB), and Digital Clock Drawing Test (DCTClock). Baseline characteristics and baseline severity will also be listed.

## 6.9. Treatment Compliance

Because dosing occurs at study visits, patients who attend all visits and successfully receive LY3303560 or placebo infusions are automatically compliant with this treatment. Any infusion at which 75% (approximately 190 mL) or more of the infusion solution is given will be considered a complete infusion.

Summary statistics for LY3303560 treatment compliance will be provided for the total number of complete infusions received, duration of complete infusion, and volume of complete infusion by treatment group. Frequencies and percentages of reasons why infusion was stopped will also be presented.

## 6.10. Concomitant Therapy

Prior medications are defined as those that stop before randomization (the day prior to the first administration of study drug). Concomitant medications are defined as those being taken on or after randomization (the day prior to the first administration of study drug). A summary of concomitant medications will be presented as frequencies and percentages for each treatment group. Fisher's exact test will be used to test for treatment differences between groups. If the start or stop dates of therapies are missing or partial to the degree that determination cannot be made of whether the therapy is prior or concomitant, the therapy will be deemed concomitant. A summary table will also be provided for concomitant AChEI/memantine medications.

Medications will be coded using the World Health Organization (WHO) drug dictionary. Concomitant medications will be listed.

## 6.11. Efficacy Analyses

### 6.11.1. Primary Outcome and Methodology

The primary objective of this study is to test the hypothesis that IV infusion of LY3303560 will slow the cognitive and/or functional decline of AD as measured by the composite measure iADRS compared with placebo in patients with early symptomatic AD. This will be assessed using a Disease Progression Model (DPM).

The iADRS at each scheduled visit (according to the SoA) during the treatment period will be the dependent variable. The DPM is as follows:

$$Y_{ij} = \gamma_i + e^{\theta T_i} \sum_{v=0}^j \alpha_v + \mathbf{x}'_i \boldsymbol{\beta} + \varepsilon_{ij}, i = 1, 2, \dots, k; j = 1, 2, \dots, l$$

where  $Y_{ij}$  denotes the clinical outcome at visit  $j$  for participant  $i$  and clinical outcome score at baseline (prior to treatment) is  $Y_{i0}$ .  $\gamma_i$  ( $i=1, 2, \dots, k$ ) represents the random participant effects.  $T_i$  denotes the treatment arm for participant  $i$ .  $T_i$  takes a value of 1 if a participant is randomized to the low dose, a value of 2 for high dose, and a value of 0 for placebo.  $e^{\theta T}$  is the disease progression ratio (DPR) for treatment  $T$  and  $e^{\theta T} = 1$  for placebo.  $e^{\theta 1}$  and  $e^{\theta 2}$  represent the DPR of the low dose and the high dose, respectively. Furthermore,  $\alpha_v$  is the change in mean cognitive score for placebo from visit  $v-1$  to  $v$ .  $\varepsilon_{ij}$  is the error term. Additional covariates  $\mathbf{x}_i$  will include pooled site ID, age, and baseline AChEI/memantine use (yes/no).

The DPM model assumes the treatment effect of LY3303560 is proportional to placebo over the course of the study. This proportionality assumption is similar to the assumption made in proportional hazards modeling of time to event data. The DPM includes generally diffuse priors on all parameters. The precision value for the prior distribution of all parameters is set to a small value; therefore, the prior distributions on all parameters have very little impact on the posterior distributions. No information or knowledge of the effect of LY3303560 from previous studies will be incorporated into the prior distributions, and the inference will be based on Study LMDC only. Diffuse priors will be used.

For subject level random effect  $\gamma_i \sim N(\mu_\gamma, \sigma_\gamma^2)$ , a diffuse normal prior is assumed for  $\mu_\gamma$ , the mean of the subject level random effect and a diffuse inverse gamma prior is considered for  $\sigma_\gamma^2$ , the variance of the subject level random effect:

$$\mu_\gamma \sim N(0, 10^2), \sigma_\gamma^2 \sim IG(0.005, 0.005).$$

A diffuse normal prior distribution is assumed for each mean change in disease progression from visit  $v - 1$  to visit  $v$  in the placebo,  $\alpha_v$ :

$$\alpha_v \sim N(1.25, 900)$$

A normal prior distribution  $N(0,4)$  is assumed for the  $\log(\text{DPR})$  parameter of each active treatment arm (i.e.,  $\theta_1$  and  $\theta_2$ ). For the error term  $\epsilon_{ij} \sim N(0, \sigma_\epsilon^2)$ , an inverse gamma prior is assumed for the model error variance:

[figure not shown]
$$\sigma_\epsilon^2 \sim IG(0.005, 0.005).$$

Diffuse normal prior of the form  $N(0,100)$  is used for each baseline covariate (pooled site ID, age and baseline AChEI/memantine use (yes/no)) in the model. A DPR less than 1 favors LY3303560 and corresponds to a slowing of disease progression with LY3303560 in comparison to placebo; similarly, a DPR greater than 1 favors placebo. The DPM will be fit to the data and Bayesian inferences will be summarized including posterior distribution of DPR and posterior probabilities of various DPR thresholds of interest (for example, 0.75 which translates to 25% slowing of disease progression with LY3303560 group versus placebo). To test the hypothesis of a disease progression benefit, we calculate the posterior probability of superiority in cognitive/functional slowing and if it is above a pre-specified threshold (which controls the false positive rate at the values in the graphical testing scheme), then a claim of cognitive/functional slowing will be made. The null hypothesis is that the DPR between the LY3303560 group versus placebo equals 1.

In addition, Bayesian posterior probability of active treatment arm being superior to placebo by at least a margin of interest will also be calculated assuming a noninformative prior.

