### **6.11.2. Gated Secondary Efficacy Analyses**

Bretz's graphical approach may be utilized to provide strong control of the study-wise type I error rate for the primary and key secondary hypotheses at a two-sided alpha level of 0.05 (Bretz et al. 2009, 2011). The DPM analyses will be conducted on the iADRS, CDR-SB, ADAS-Cog13, iADL and MMSE scores, and statistical significance will be determined based on the following multiplicity graph of hypotheses regarding the IV infusion of LY3303560 slowing the cognitive and/or functional decline of AD:

iADRS = DPM analysis of iADRS

CDR-SB = DPM analysis of CDR-SB

iADL = DPM analysis of iADL

ADAS-Cog13 = DPM analysis of ADAS-Cog13

MMSE = DPM analysis of MMSE

The preceding graphical testing scheme is outlined using alpha levels in a frequentist testing paradigm. The primary efficacy analysis for this trial is the Bayesian DPM. The following describes how probability thresholds will be developed for each test (and potential test) in the graph that control the false positive rate at the appropriate corresponding alpha level. The tests for each scale will all be of the form  $\Pr(\text{DPR} < 0.75) > X$ , where the value of X is determined via simulation to control the test at the corresponding alpha level.

To test the hypothesis of a disease progression benefit, the posterior probability of superiority in cognitive/functional slowing will be calculated, and if it is above a pre-specified threshold (which controls the false positive rate at approximately 2.5%), then a statistical significant claim of cognitive/functional slowing will be made. Success will be declared at a graphical node if the posterior probability of at least 25% slowing is greater than a certain threshold, where the threshold is determined via simulation to control the false positive rate under the null scenario for a given scale. The null scenario used in these simulations to determine the posterior probability thresholds will be the overall mean trajectory from the blinded LMDC trial data, conducted at a date late in the trial but prior to unblinding. As a sensitivity analysis of the selected posterior probability thresholds, additional simulations may be run after unblinding using the unblinded data to understand the impact of the choice of variance-covariance matrix and mean placebo trajectory on the posterior probability thresholds used to control the false positive rate.

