Assuming the null scenario of 0% slowing in treated arms relative to the placebo, synthetic data are sampled from a multivariate normal distribution for each endpoint that accounts for the correlation between visits after adjusting for concomitant drug use, pooled site, and age. The mean trajectory and variance-covariance matrix for each scale is the overall (i.e. treatment-naïve) least-squares mean (from frequentist MMRM analyses adjusting for pooled site, baseline AChEI/memantine use and age) at each visit in the blinded trial data. The Bayesian DPM is fit to each simulated dataset and the posterior probability of at least 25% slowing is calculated. The threshold is the value at which approximately  $(\alpha/2 \times 100)\%$  of the simulated posterior probabilities are larger. The cutoff for the primary analysis of LY5600 is 0.51 ( $\Pr(\text{DPR} < 0.75) > 0.51$ ); the cutoff for LY1400 is 0.99928 ( $\Pr(\text{DPR} < 0.75) > 0.99928$ ). The other thresholds will be calculated in the same way.

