### **6.11.3. Additional Exploratory Analyses of the Primary Outcome**

#### **6.11.3.1. Mixed Model Repeated Measures (MMRM)**

The change from baseline score on the iADRS at each scheduled postbaseline visit (according to the Schedule of Activities) during the treatment period will be the dependent variable. The model for the fixed effects will include the following terms: baseline score, pooled site, treatment, visit, treatment-by-visit interaction, baseline-by-visit interaction, concomitant AChEI and/or memantine use at baseline (yes/no), and age at baseline. Visit will be considered a categorical variable. The null hypothesis is that the contrast between the LY3303560 group versus placebo at the Visit 28, Week 104 (4 weeks after the final dose of LY3303560) equals zero. An unstructured covariance matrix will be used to model the within-subject variance-covariance errors. If the unstructured covariance structure matrix results in a lack of convergence, the following tests will be used in sequence: heterogeneous Toeplitz covariance structure, heterogeneous autoregressive covariance structure, heterogeneous compound symmetry covariance structure, and compound symmetry covariance structure. The Kenward-Roger approximation will be used to estimate the denominator degrees of freedom.

The primary time point for treatment comparison will be at Week 104. The treatment group contrast in least-squares mean change from baseline score on the iADRS scale and its associated p-value and 95% CI will be calculated for treatment comparisons of LY3303560 versus placebo using the MMRM model specified above.

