#### **6.11.3.2. Natural Cubic Spline**

In addition to the DPM and MMRM models described above, the iADRS will be modeled using natural cubic splines (NCS) (Chambers and Hastie 1992). The postbaseline score on the iADRS at each scheduled postbaseline visit (according to the Schedule of Activities) during the treatment period will be the dependent variable, and the mean for each treatment group over the entire double-blind duration of the study will be modeled. The NCS model provides a type of smoothing function to the data, can adequately estimate longitudinal trajectories under a variety of shapes (e.g., linear, quadratic, etc.) for each treatment group, and is thought to be a more

natural parameterization than modeling the mean change from baseline over time. The degrees of freedom of the model can be prespecified to establish the level of smoothing of the data. The number and location of the “knots” are utilized to parse out different time periods where the data may transition from one shape to another to provide an adequate fit. The primary time point for treatment comparison will be at Week 104. The variance-covariance structure assumptions of the NCS model are the same as the MMRM model and the covariates used in the model would remain unchanged. The model would be estimated by restricted maximum likelihood using SAS PROC MIXED or the `gls` function from the `nlme` package in the R.

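### The DPM assumes compound symmetry: the simulated cutoffs protect each pass/fail decision, but the reported DPR posterior would be too certain if patients diverge over time

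*SAP*

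**What the plan says.** Section 6.11.1 writes the outcome as a random patient effect, plus a DPR times the cumulative placebo change, plus covariates, plus an error term. The patient effect is one normal intercept. For the error, "an inverse gamma prior is assumed for the model error variance", with the same variance at every visit. There is no random slope and no visit covariance.

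The same section commits to reporting the "posterior distribution of DPR and posterior probabilities of various DPR thresholds of interest", with 0.75 as an example, and adds that a "Bayesian posterior probability of active treatment arm being superior to placebo by at least a margin of interest will also be calculated".

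Section 6.11.2 tests each scale by Pr(DPR<0.75) against a cutoff found by simulation under no effect, where "synthetic data are sampled from a multivariate normal distribution for each endpoint that accounts for the correlation between visits". The covariance comes from an MMRM on the blinded trial data. The printed iADRS cutoffs are 0.51 for the high dose; for the low dose, "the cutoff for LY1400 is 0.99928". Further simulations after unblinding are optional and are meant to "understand the impact of the choice of variance-covariance matrix and mean placebo trajectory on the posterior probability thresholds".

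The companion analyses of iADRS do not share the restriction. In section 6.11.3.1, "An unstructured covariance matrix will be used to model the within-subject variance-covariance errors". In section 6.11.3.2, "The variance-covariance structure assumptions of the NCS model are the same as the MMRM model". A DPM also appears in sections 6.1.1 (COVID-19 censoring), 6.11.3.8 (per protocol) and 6.14 (subgroups), with no cutoff given.

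**The concern.** A random intercept with constant independent error implies the same variance at every visit and the same correlation between any two visits. In a progressive disease, patients may decline at different rates, so variance grows and distant visits correlate less than adjacent ones. The DPM would then treat persistent differences in rate as visit-to-visit noise that averages out over the schedule, and its posterior for the DPR would be too narrow.

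The cutoffs fix this for one event per node: whether Pr(DPR<0.75) exceeds X when there is no effect. They do not make a DPR interval, Pr(DPR<1), or a reported 95% probability of at least 25% slowing mean what it says. A reader will tend to take such figures at face value for iADRS, CDR-SB, ADAS-Cog13, iADL and MMSE. Where the DPM is used without a cutoff, the posterior is all that model offers.

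**Working it through.** **Inputs from the SAP.** Section 5.2: 360 patients, 30% dropout, placebo decline 19.56, slowing of 33% and 50%, Week 104 variance 436.85 (SD 20.9), success rule of at least 0.6 in at least one arm, power above 95%, false positive rate about 2.5%. Section 6.11.1: model and priors. Section 6.11.2: cutoffs 0.51 and 0.99928.

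**Assumed, because the SAP does not give them.** Number and spacing of visits, baseline SD, residual SD, and the form of divergence (random slope or random walk).

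**1. What the model implies.** Var(Y) = σγ² + σe² at every visit; Corr = σγ²/(σγ² + σe²) for every pair. With a baseline SD of 13, variance would instead grow from 169 to 436.85, a factor of 2.6.

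**2. The plan's own figures.** A simple Week 104 comparison has 120 × 0.7 = 84 completers per arm and SE = 20.9 × √(2/84) = 3.22. Differences of 9.78 and 6.45 give power of 85.8% and 51.7%, and about 88.5% for either arm. That is below 95% because it ignores the earlier visits. Simulating the DPM itself (nine equally spaced visits including baseline, random slopes):
- Baseline variance 120 to 180 and residual variance 40 to 100 give a false positive rate of 2.0% to 3.4% for the 0.6 rule. Power, run at 180 and 40 with the 3-month delay, is 99%. Both stated figures are reproduced.
- Baseline variance 250 with residual variance 40 gives a false positive rate of 0.4%. True compound symmetry at variance 436.85 (residual variance 100) gives 0 in 1,500.

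Under these assumptions, the stated 2.5% fits diverging patients better than exchangeable ones.

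**3. Size of the overconfidence.** Let r = posterior SD / true sampling SD. Approximate coverage of a nominal 95% interval is 2Φ(1.96r) − 1. Large-sample (sandwich) results, 4 to 8 post-baseline visits, 30% dropout:

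| Baseline SD | Residual SD | r | Coverage |
|---|---|---|---|
| 13 | 6–8 | 0.44–0.67 | 61–81% |
| 16 | 6–12 | 0.52–0.79 | 69–88% |
| 18 | 8–12 | 0.67–0.85 | 81–91% |
| 20 | range tried | 0.76–0.94 | 86–93% (by the formula) |
| Exchangeable truth | – | 1.00 | 95% |

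At baseline SD 13, r did not change with sample size (75 or 120 per arm, covering the 225 on the title page and the 360 of section 5.2) or with decline (16 or 19.56). It barely moved with dropout of 0–40% or curved decline (0.44–0.68). Baseline SD is the input that matters most.

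**4. Full Bayesian fits with the stated priors.** Baseline SD 13, no covariates, 400 trials per setting. The last two columns give how often Pr(DPR<0.75) exceeds 0.95 when the true DPR is exactly 0.75.

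| Truth | Posterior / sampling SD (null) | Coverage (null) | Plan's DPM | Unstructured DPM |
|---|---|---|---|---|
| Slope, 8 visits | 0.065 / 0.147 | 62.1% | 23.9% | 6.2% |
| Slope, 6 visits | 0.068 / 0.139 | 67.7% | 22.6% | 8.3% |
| Random walk, 4 visits | 0.098 / 0.140 | 82.0% | 15.2% | 7.7% |
| Exchangeable | 0.075 / 0.077 | 93.8% | 8.5% | 8.3% |

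The unstructured fits are maximum likelihood on 200 of the same trials; their null coverage is 93.0% to 94.5%. At a true DPR of 0.75 the plan's DPM covers 63.1%, 67.0%, 82.8% and 93.8%, so coverage measured under the null carries over. The fair comparator is the correctly specified fit at 6–8.5%, not the nominal 5%. The excess is 23.9/6.2 = 3.9, 22.6/8.3 = 2.7 and 15.2/7.7 = 2.0 times.

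**5. The printed cutoffs.** Under the null both doses have the same sampling distribution, so the cutoffs differ only through alpha. Under normality r = (z_low − z_high) / (z(0.99928) − z(0.51)) = (z_low − z_high) / (3.187 − 0.025). Taking z_high = 1.96 (two-sided 0.05, the most generous choice), low-dose two-sided alphas of 0.01, 0.001, 0.0001 and 0.00001 give r = 0.19, 0.42, 0.61 and 0.78. For r = 1 the low-dose alpha would have to be about 3 × 10⁻⁷.

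**The case against.** The strongest reply is that no decision is affected. Every node's cutoff comes from fitting this same DPM to data with a realistic visit covariance, so the error rate of each confirmatory claim already allows for the misfit. That stands. A reader might infer that the restriction inflates the trial's false positive rate, or that the DPM and the MMRM contradict each other. The SAP supports neither: the cutoffs do their job, and two models may have different covariances. Nor is Pr(DPR<0.75) wholly uncalibrated, since it is tied to the null at one point per node.

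Second, sections 6.11.3.1 to 6.11.3.3 and 6.11.4 give checks that do not rest on compound symmetry. This softens the concern, but they address score differences and not the DPR.

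Third, the size depends on a baseline SD that the SAP does not state. That stands, and is why a range is shown. The cutoff pair is consistent with overconfidence but cannot size it, because the alpha split lies in a graph that is not readable in the text available.

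Fourth, sections 6.11.3.8 and 6.14 are not plainly the section 6.11.1 model: they list treatment-by-visit terms, the former analyses change from baseline, and neither states a covariance. Section 6.1.1 runs the MMRM alongside. None of the three makes a multiplicity-controlled claim, so the point there is only one of labelling.

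**Conclusion.** The concern holds as a reporting gap of minor to moderate severity. The direction is secure if between-patient variance grows over time; no diverging case tried reversed it. With an assumed baseline SD of 13 to 16 and residual SD of 6 to 12, the posterior SD is about 0.45 to 0.8 of the true SD and nominal 95% intervals cover about 62% to 88%. At baseline SD 13 and a true DPR of 0.75, a reported probability above 0.95 arises in about 15% to 24% of trials, against 6% to 8.5% for a correctly specified fit. The error shrinks as the baseline SD nears 20.9 and vanishes under exchangeable covariance. The magnitude is illustrative: it rests on assumed visits, baseline and residual SDs, and on simulations without the site, age and AChEI/memantine covariates.

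**What to change.** Keep the primary DPM and its cutoffs. In sections 6.11.1 and 6.11.2 add:

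1. The simulated coverage of the primary DPM's 95% DPR interval for each scale, taken from the threshold simulations already planned.
2. A prespecified supportive DPM with unstructured visit covariance for iADRS and the four gated scales, with a stated diffuse covariance prior. If it does not converge, fall back only to structures with visit-specific variances (heterogeneous Toeplitz, then heterogeneous autoregressive). The list in section 6.11.3.1 cannot be borrowed whole, because it ends in compound symmetry. Report this DPR posterior beside the primary one, as supportive only.
3. A sentence that posterior probabilities from the primary DPM are calibrated only through the simulated cutoffs and are not to be read at face value.

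In sections 6.1.1, 6.11.3.8 and 6.14, label the DPM results as descriptive.

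Cost: SAP text before the lock, one extra fit per scale (five in all) with longer MCMC runs, and one extra output from existing simulations. Supportive posteriors would be about 1.5 to 2.2 times wider at baseline SD 13, and there would be two DPR posteriors to explain. The supportive model was tried here only by maximum likelihood, so its Bayesian version needs a short check. Nothing that decides the trial changes after the unblinded efficacy interim.
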